5.3.1.5. Safety and tolerability

It is now recognized that topical corticosteroids can lead to an increase in PIO. It is possible to present ocular hypertension in a repeated dose treatment as soon as in a week, an effect that may

be more pronounced in glaucomatous eyes. [44] Prolonged elevation of the PIO is associated with damage to the optic nerve, with subsequent alteration of the visual field and possibly AV.

Another well-documented effect of steroid use includes the formation of posterior subcapsular cataracts and the predisposition to ocular infections.

Studies previously reported have shown that DFBA causes an increase in PIO in a small number of exposed patients. This increase was resolved in all patients upon discontinuation of treatment or with the help of topical hypotensives. Compared with betamethasone and prednisolone applied with the same frequency, the incidence of PIO elevation was equal, indicating an acceptable safety profile. [44] [49] [48] [50]

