6.2 Eligibility criteria.

6.2.1 Inclusion criteria.

- Signed informed consent.
- Age ≥ 18 years.
- Both sexes.
- Postoperative cataract surgery by phacoemulsification.
 - o That they have met the criteria for phacoemulsification and a classification of the LOCS III cataract of NO ≥ 2 and NC ≥ 2 .

6.2.2 Exclusion criteria.

6.2.2.1 General criteria.

- Pregnant women, lactating or planning to get pregnant.
- Women of reproductive age and who do not have a hormonal contraceptive method, intrauterine device or bilateral tubal obstruction.
- Participation in another clinical research study ≤ 30 days before the baseline visit.
- Have previously participated in this same study with the contralateral eye.
- That they can not comply with their attendance at appointments or with all the requirements of the protocol.

6.2.2.2 Medical and therapeutic criteria.

- Surgery in both eyes in the same surgical shift.
 - Time > 24 hours after having surgery.
 - LIO placement outside the bag.
 - Presentation of rupture of the posterior capsule, with or without the presence of vitreous.
 - Carrying out an iridectomy, or lesion of the pupillary sphincter during phacoemulsification surgery.
 - Scheduled for surgical intervention in the contralateral eye during the study period.
 - History of glaucoma or ocular hypertension.
 - History of increased PIO with the use of steroids.
 - PIO ≥ 24 .
 - History of uveitis.
 - Presence of corneal abrasion or corneal ulceration in the study eye.
 - Use of steroids or topical NSAIDs, 24 hours prior to surgery and until the start of instillation of investigational drugs.
 - Use of anticoagulants, systemic steroids or immunomodulators in the last two weeks
 - Periocular injection of any steroid in the study eye 4 weeks before the start of the instillation of the investigational drugs.
 - Use of storage steroids 2 months prior to the start of instillation of investigational drugs.
 - Presence or suspicion of keratitis and / or viral, bacterial or fungal conjunctivitis.
 - Presence or suspicion of endophthalmitis.
 - Presence or suspicion of toxic syndrome of the anterior segment.
 - Severe corneal edema that does not allow assessment of the anterior chamber
 - Macular diseases.
-
- Diabetes Mellitus with A1C $\geq 6.5\%$ (48 mmol / mol) or fasting glucose (no caloric intake by ≥ 8 hours) of ≥ 126 mg / dL (7.0 mmol / L).
 - Any disease or condition that requires the use of topical or systemic NSAIDs during the time of intervention.

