 - Any disease or condition that requires the use of steroids other than topical ophthalmic application.
 - Subjects with a single eye.
 - Any condition or disease that at the discretion of the IP does not make the subject suitable for the study.
 - Known hypersensitivity to the components of the products under investigation.

6.2.3 Elimination criteria.

- Decision of the subject. The subject can decide unilaterally to withdraw from the study at any time, should inform the IP.
- Pregnancy.
- Presence of a serious adverse event (EAS).
- Investigator's decision:
 - o Due to the presence of an AD that at the discretion of the IP threatens the health of the subject and requires the prescription of a medicine not authorized in the protocol
- Any deviation to the protocol that affects the safety of the subject.

6.2.4 Identification of the subject.

The patients of the study will be identified by a number and the initials of their name.

The initials of the study subject will be obtained by starting with the first letter of the name, followed by the first letter of the first surname and the first of the second, obtaining maximum three letters, in case the person has two names or a compound surname will always be used the first letter of the first name or last name composed.

Example:

1. Adolfo Daniel Mercado Carrizales

to. Initials: AMC

2. Juan De la Torre Orozco

to. Initials: JDO

[figure not shown]
3. Luis Carlos Pérez-Gómez Ramírez

to. Initials LPR

In the counting stage, the participant number will be assigned consecutively, using 3 consecutive digits. Once the subject has been selected, he will be assigned a number with which he will be identified throughout the study. Said code will be composed of eight numbers in the following order from left to right:

- three digits of the molecule under study according to the denomination by the sponsor.
- two digits corresponding to the research center number
- three digits of the number consecutive to their inclusion assigned in the research center.

Example:

6.3 Intervention .

6.3.1 Managed treatments.

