There is no standardized parameter to define an adequate adherence, it must be defined and outlined by the objectives of the research in particular. [62] The efficacy of ophthalmic steroids is based on two fundamental principles: 1) The specific type and location of the inflammation determines the appropriate route of administration and 2) The treatment should be instituted as soon as possible, and the dose should be high enough and administration frequent enough to suppress inflammatory activity. According to the therapeutic utility curve, to establish the limits of the therapeutic window, a dosage regimen is required in which 50% of the established doses are exceeded, in order to achieve a pharmacological effect. A therapeutic regimen below this value is expected a lack of efficacy. Therefore, an adherence of over 60% according to the weight of the bottle ensures that it remains within the limits of efficacy of the therapeutic window established in the protocol. [64] [65] [66] For the efficacy analysis, only subjects with a minimum adherence of 80% by means of the subject's daily tool and a minimum of 60% by the weight of the bottle will be considered. The variation in the percentage of the measurement method has been chosen empirically to counteract the sensitivity and specificity of the same. It is estimated that with a minimum adherence of 60% the intervention can exert its expected anti-inflammatory pharmacological action. [44]

6.3.3 Treatments and concomitant interventions allowed and prohibited before and during the study.

The subjects admitted correctly to the study, who meet the eligibility criteria, may continue with the systemic treatment of the underlying diseases. If during the development of the study they require the implementation of a new permitted medication, they may do so. All concomitant medications used must be duly reported in the notes of the clinical file and in the corresponding section.

Allowed medications:

- Ophthalmic:
- All permitted medications applied via ophthalmic during the study, must wait a minimum period of 10 minutes from the last application of the treatments under study or reference. The foregoing in order to avoid the interaction of the treatments in the tear film, based on the tear flow index and the physiological tear volume. [67]
 - Tetracaine 0.5%
 - Tropicamide 0.8% / Phenylephrine 5%
 - Any antibiotic
 - Beta-blockers
 - Alpha agonists
- Administered by a different route to ophthalmic:

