 - Medications whose effect may be susceptible to modify any of the parameters of efficacy, safety or tolerability of this research protocol should notify their clinical monitor or scientific committee of the sponsor to judge the convenience of entry, continuation or elimination of the participant as appropriate.

Any medication allowed that is used, besides appearing in the clinical note, must be registered in the section of concomitant medications in the CRF.

- Prohibited medications:
- Any medication with ophthalmic application that is not on the list of allowed medications
- Systemic steroids
- Systemic NSAIDs
- Systemic immunomodulators
- Anticoagulants.

6.3.4 Treatment management.

The treatments will be provided by Sophia Laboratories, S.A. of C.V., for each research center. They will be labeled and reconciled. The handling of the treatment will be under the responsibility of the IP or a designated member of his team.

6.3.4.1 Delivery and reception.

The sponsor will be responsible for delivering the study treatments at the research center according to internal procedures. The delivery will be made in closed boxes by means of a courier service or directly by the sponsor's staff to the address of the research center according to the study plan.

The reception will be exclusively carried out by the research center team, including the IP. You must check the good condition of the primary packaging (box). In the event that it shows alterations or defects in its integrity that from its judgment could have damaged the content, it should report it to the sponsor. If the package does not show significant defects, it will proceed to open it.

Inside you must locate the acknowledgment document and the logger (data logger) of temperature and humidity. You should check that the registered temperature and humidity comply with the specifications for transport and shelter (see 6.3.4.2 Storage). Subsequently verify the content (treatments) with what is reported in the document. In case the document corresponds to the content, it will sign the receipt and send it to the sponsor. Otherwise, notify the sponsor.

In the study center, the personnel assigned by the IP will deliver the corresponding treatment to the inpatients. The center must register the medicine delivered.

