6.3.4.2 Storage

The medication must be stored in a secure area with restricted access. Storage should be at room temperature to no more than 30 ° Celsius.

The research center has the obligation to record, in the format designated by the sponsor, the temperature and humidity registered in the data logger. This record should include the current temperature and humidity, as well as the minimum and maximum of each of these. It must be done at least once a day, on business days.

Said data will be compared by the clinical monitor according to the registration in the data logger.

6.3.4.3 Return.

The research subjects will return, to the personnel indicated by the IP in the center, their treatments in the final visit.

The refund will be made by the research center when the sponsor indicates it. Prior to the return the research center must make a count of the assigned medication and the remaining medication, with the aim of creating an inventory which serves for the final filling of the medication return form.

6.4 Outcome variables.

6.4.1 Security variables.

6.4.1.1 Primary outcome variables.

Visual ability

Adverse events

Intraocular pressure.

6.4.1.2 Tolerability variables.

Symptomatology postinstillation

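### Intraocular pressure is a primary safety variable, but the plan has no pressure event and no rule for readings taken on permitted pressure-lowering drops, so a real later-visit difference between arms would be attenuated

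*Combined protocol and SAP*

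**What the plan says.** Section 6.4.1.1 names "Intraocular pressure" as one of three primary safety variables, beside visual ability and adverse events. Table 5 in section 6.4.3 classes it as continuous, in mmHg. Tonometry is scheduled at baseline, day 7, day 14 and the final visit on day 29 (section 6.5.1).

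Section 6.3.3 allows two classes of pressure-lowering drop, "Beta-blockers" and "Alpha agonists". It also says: "If during the development of the study they require the implementation of a new permitted medication, they may do so". Section 5.3.1.5 describes what such drops did to steroid-induced rises in earlier studies: "This increase was resolved in all patients upon discontinuation of treatment or with the help of topical hypotensives".

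Section 6.2.2.2 excludes "History of glaucoma or ocular hypertension", a previous pressure rise on steroids, and an entry IOP of 24 or more.

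Use of the drops is recorded: "Any medication allowed that is used, besides appearing in the clinical note, must be registered in the section of concomitant medications in the CRF". The duty to tell the sponsor about drugs that may alter a safety parameter sits under non-ophthalmic routes, so it does not reach these drops. The elimination rule in section 6.2.3 applies to an adverse event that threatens health and "requires the prescription of a medicine not authorized in the protocol". Starting an allowed drop does not trigger it.

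For analysis, section 8.3.1 gives continuous variables a mean, SD and range and a t test between groups, and reports adverse events as numbers of cases. Section 8.3.2 adds an unspecified internal analysis of changes between visits. Section 8.3.3 puts every subject exposed at least once in the safety assessment. None of the three mentions pressure-lowering drops, an IOP threshold, an IOP time point, or each subject's highest reading.

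**The concern.** The trial compares two topical steroids, and raised IOP is a class effect that the protocol itself describes. A subject whose pressure rises may receive an allowed drop and stay in the study. The readings that follow measure the steroid plus the drop. Known glaucoma, ocular hypertension and previous steroid response are excluded at entry, so most drops started on study will reflect rises that occurred on study. Drop use is therefore outcome information, and the analysis sections leave it out.

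If one arm has more responders, it also receives more drops, and its later mean is pulled down further. The final-visit comparison can then look reassuring because the rises were treated, not because they did not occur. For a safety variable, that is the unhelpful direction of error.

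**Working it through.** **No figure to reproduce.** The documents give no responder rate, SD, drop-use rate or sample-size calculation for IOP. The one computed sample size concerns efficacy and does not bear on this point.

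**Which readings are affected**

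| Reading | Status under the plan |
|---|---|
| Before drops, including a raised one at a scheduled visit | Kept; no rule says how it enters the comparison |
| After drops start, including the final visit | Kept, lowered, pooled with untreated readings |
| Before elimination | Kept (section 8.3.3) |
| After elimination | Absent |

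**Size, on assumptions only.** Take 89 per arm (section 6.6), a rise of 12 mmHg in responders, SD 3 mmHg around each subject's expected value, and a two-sided 5% independent-samples t test. Let p be an arm's responder proportion and m the proportion of responders returned to normal by drops in both arms. Those still raised are q = p(1 − m).

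- Observed mean difference = 12 × (pT − pC) × (1 − m).
- Variance in an arm = 3² + 12² × q(1 − q).
- Standard error = √[(varT + varC)/89].

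Worked case: 10% against 3%, no masking.

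- Difference = 12 × 0.07 = 0.84 mmHg.
- Variances = 9 + 144 × 0.10 × 0.90 = 21.96, and 9 + 144 × 0.03 × 0.97 = 13.19.
- Standard error = √(35.15/89) = 0.628, and 0.84/0.628 = 1.34.
- Approximate power = Φ(1.34 − 1.96) = Φ(−0.62), about 27%. Simulating the skewed mixture gives about 26%.

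Simulated t-test power (separate runs agree within about one percentage point):

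| Responders | Masked (m) | Mean difference, mmHg | Still raised per 89, by arm | t-test power |
|---|---|---|---|---|
| 10% vs 3% | 0% | 0.84 | 8.9 vs 2.7 | 26% |
| | 50% | 0.42 | 4.5 vs 1.3 | 11% |
| | 80% | 0.17 | 1.8 vs 0.5 | 6% |
| | 100% | 0 | 0 vs 0 | 5% |
| 15% vs 3% | 0% | 1.44 | 13.3 vs 2.7 | 56% |
| | 50% | 0.72 | 6.7 vs 1.3 | 23% |
| | 80% | 0.29 | 2.7 vs 0.5 | 8% |
| | 100% | 0 | 0 vs 0 | 5% |

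If starting drops for raised IOP counts as an event, masking does not remove it. Exact enumeration of Fisher's test gives power of 36% at 10% against 3%, and 77% at 15% against 3%.

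**Wider range.** With responders from 5% against 2% up to 15% against 3%, and rises of 8 to 12 mmHg, the unmasked difference is 0.24 to 1.44 mmHg. It falls to 0.12 to 0.72 at 50% masking and to 0.05 to 0.29 at 80%. The relative shrinkage equals the masked fraction throughout.

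**The case against.** A reader might infer that treated responders simply look normal, or that eliminated subjects drop out of the comparison. The documents do not support either reading. With tonometry at every visit, a rise found at a scheduled visit is recorded before drops can act, and section 8.3.3 keeps every exposed subject whatever the visit of elimination. Only later readings are lowered or lost. A planned visit-by-visit IOP comparison is also an inference, because section 8.3.1 names no IOP time point.

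There is a second channel. Adverse events are an equal primary safety variable, and section 9.3.1.1 requires the therapy for an event to be logged. A treated rise could well be counted there. The range required by section 8.3.1 would also show the highest value in a group. Both objections stand in part. With no IOP threshold, reporting a rise as an adverse event depends on each investigator, and a range shows one extreme value, not how many subjects had a rise.

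It would be tempting to set 77% against 5% and blame the drops for the whole gap. That comparison assumes every responder is normalised. Even with no masking, the t test has only about 56% there and 26% in the other scenario, so part of the gap comes from summarising a minority response by a mean.

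The attenuation also needs a true difference between arms. Section 5.3.1.5 reports equal incidence of IOP elevation against betamethasone and prednisolone at the same dosing frequency. If that holds here, there is no difference to attenuate, although treated rises would still be under-represented in both arms' later means.

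Last, observed IOP on drops is a legitimate summary of pressure under the care actually given. Replacing it with a carried-forward pre-drop value would be debatable, since section 6.5.2.3 has the steroid reduced from day 15 and an early peak may overstate pressure at day 29.

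**Conclusion.** The gap is real but limited. A primary safety variable can be altered by drugs that the protocol allows, their use is recorded, and the analysis sections neither use that record nor define an IOP event. If the arms truly differ, comparisons of readings after drops start shrink in proportion to the responders normalised: by half at 50% masking and by four fifths at 80%. Pre-drop and pre-elimination readings survive, and some rises will appear as adverse events, but no threshold or per-subject maximum ensures that either informs the comparison.

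The text establishes the gap and, given a difference, the direction. The sizes rest wholly on assumed responder rates, rise, SD and masking, and on equal masking in both arms. The documents do not show that a difference exists or that the safety signal as a whole is lost. Primary efficacy is unaffected. The plan should be changed because the repair is cheap and must be fixed before unblinding to be credible.

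**What to change.** Before unblinding, add to section 8.3:

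- **A subject-level IOP safety event**, met by any of: IOP above a limit the sponsor fixes in advance, at any visit; start of any pressure-lowering drug for raised IOP; or withdrawal for IOP. Compare arms by Fisher's exact test, with a 95% confidence interval for the difference, in all exposed subjects. Power is modest (36% in the first scenario above), so the interval matters more than the p-value.
- **A table of pressure-lowering drug use by arm.**
- **Observed mean IOP as a descriptive summary**, with a sensitivity analysis that handles on-drop readings, for example by using each subject's highest pre-drop value.

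Allowed drugs and their use do not change. The cost is SAP wording and one extra table, and the reported IOP event rate may look less favourable. IOP and concomitant medication are already collected at each visit. Section 6.5.2.1 asks for active substance, posology and duration, so the sponsor should confirm that the CRF also captures the start date and reason for each pressure-lowering drug.

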6.3.4.2 Storage

The medication must be stored in a secure area with restricted access. Storage should be at room temperature to no more than 30 ° Celsius.

The research center has the obligation to record, in the format designated by the sponsor, the temperature and humidity registered in the data logger. This record should include the current temperature and humidity, as well as the minimum and maximum of each of these. It must be done at least once a day, on business days.

Said data will be compared by the clinical monitor according to the registration in the data logger.

6.3.4.3 Return.

The research subjects will return, to the personnel indicated by the IP in the center, their treatments in the final visit.

The refund will be made by the research center when the sponsor indicates it. Prior to the return the research center must make a count of the assigned medication and the remaining medication, with the aim of creating an inventory which serves for the final filling of the medication return form.

6.4 Outcome variables.

6.4.1 Security variables.

6.4.1.1 Primary outcome variables.

Visual ability

Adverse events

Intraocular pressure.

6.4.1.2 Tolerability variables.

Symptomatology postinstillation

6.4.2 Efficacy variables

6.4.2.1 Primary outcome variables

Cellularity in the anterior chamber

6.4.2.2 Secondary outcome variables

Visual ability

Central thickness of the retina

Clinical corneal edema

Conjunctival hyperemia

Flare

Ocular symptomatology (pain and photophobia)

6.4.3 Methods and scales to be used for the measurement of the variables

The variables and their units of measurement are included in **Table 5 Method of measuring variables**

Variable	Unity	Symbol	Type	Method of measurement
Visual ability	Decimals	---	C. Continuous	Primer
Cellularity in the anterior chamber	Degrees	---	C. Ordinal	Direct observation (Biomicroscopy)
Clinical corneal edema	Degrees	---	C. Ordinal	Direct observation (Biomicroscopy)
Adverse events	Number of cases	N	C. Discrete	Count
Flare	Degrees	---	C. Ordinal	Direct observation (Biomicroscopy)
Central thickness of the retina	microns	μm	C. Continuous	Optical coherence tomography
Conjunctival hyperemia	Degrees	---	C. Ordinal	Direct observation (Biomicroscopy)
Intraocular pressure	Milimeters of mercury	mmHg	C. Continuous	Tonometry by Goldman applanation
Symptomatology	points	---	C. Discrete	Interrogation

Table 5 Method of measuring variables.

The following describes the methods and scales that will be used for the measurement of the variables, which are in strict alphabetical order of the procedure:

6.4.3.1 Biomicroscopy

It is the procedure by which, with the use of the slit lamp or biomicroscope, the ocular structures are evaluated thanks to the characteristics of the light source and the optical power of the instrument. A full assessment of the previous segment will be made, which will be recorded in the clinical file.

By means of biomicroscopy, **conjunctival hyperemia, clinical corneal edema, anterior chamber cellularity and flare will be evaluated.**

Conjunctival hyperemia is defined as the simplest reaction of the conjunctiva to a stimulus, a red appearance secondary to the vasodilation of the conjunctival vessels of variable intensity. He will

graduate using the Efron scale. [68] The number will be reported in the CRF, according to the rating granted. (See Illustration 2)

Illustration 2. Efron scale for conjunctival hyperemia.

Corneal edema and transparency is evaluated regularly using the biomicroscope since it offers the advantage of variable magnifications and lighting techniques, the subjective evaluation of edema is limited to the observation of signs such as microcysts, striae and folds and perhaps the comparison of opacity corneal against images of graduation scales. The transparency of the healthy cornea results from the fact that it does not absorb light and its light scattering is minimal, so that an inflamed cornea does not maintain these characteristics. [69]

Although several methods have been described in the academic literature for the clinical evaluation of inflammation and corneal transparency, there is not one that has been accepted internationally or has a widespread use in clinical practice. For the present protocol we will use the Efron scale, which is a series of pictorial sections of the cornea, including features such as grooves and folds. [68] The Efron scale has a strong correlation with variations in intensity. [69] The number will be reported in the CRF according to the rating awarded. (See Illustration 3)

Illustration 3. Efron scale for corneal edema

In the presence of intraocular inflammation, the increased permeability of the non-pigmented layer of the ciliary epithelium, the posterior epithelium of the iris and the vascular endothelium of the iris results in the accumulation of cells and proteins (visible to the examiner as flare) in the anterior chamber. Using a light beam of 0.2mm X 0.2mm directed obliquely to the anterior chamber with a forward inclination of the light source (slit lamp tower) the degree of flare and cellularity will be determined according to the group of work of standardization for the nomenclature of uveitis. [70] The degree of agreement to the granted rating will be reported in the CRF. (See Table 6 and Table 7)

Table 6. Scale for anterior chamber cellularity.

Grade	Number of cells
0	Any

½ +	1-5
1 +	6-15
2 +	16-25
3 +	26-60
4 +	More than 60

Visible in a field of 0.2mm x 0.2mm

Table 7. Flare scale

Grade	Number of cells
0	There is no flare
1 +	Mild
2 +	Moderate (iris and crystalline clearly visible)
3 +	Marking (iris and crsitalino slightly blurred)
4 +	More than 60 (fibrin)

6.4.3.2 Visual ability.

Visual acuity (AV) is a test of visual function. Spatial visual acuity is the ability to distinguish separate elements of an object and identify them as a whole. It is quantified as the minimum separation angle (located at the nodal point of the eye) between two objects that allows perceiving them as separate objects.

Snellen's notation is described as the distance at which the test is performed, divided by the distance at which the letter is vertically equivalent to 5 arc minutes. Thus, at 6 meters a letter 6/6 (20/20) equals 5 minutes of arc, a letter 6/12 (20/40) equals 10 minutes, and a letter 6/60 (20/200) equals 50 minutes. The Snellen fraction can also be expressed as a decimal (ie 20/20 = 1 and 20/40 = 0.5). [71]

The AV will be evaluated basally, without refractive correction with the Snellen chart. Which will be located in a place with adequate lighting, natural or artificial and at a distance of 3m from the subject to be evaluated. The visual acuity of each eye will be taken, starting with a right eye (OD) asking the subject to keep both eyes open and using an occluder to cover the left eye (OS); the subject will read aloud the lines that the evaluator points out, the line of smaller letters that he reaches to see will be annotated by the fractional evaluator as the AV of the OD in the clinical record. Proceed to the OS with the same method.

Subsequently the best refractive correction of the subject will be made and the examination will be repeated using the obtained refraction. This result will be reported as visual capacity (CV), it will be recorded as a fraction in the clinical file and in the CRF, and in the CRF it will be written in decimal. By definition, the CV can not be inferior to the AV.

6.4.3.3 Evaluation of adverse events.

The evaluation of adverse events requires a questioning conducted by the IP and the appropriate exploratory techniques for its detection.

The IP will record in the corresponding section of the CRF the EAs that the subjects of the study will present.

The management of the EAs will be done according to what is described in section 9.3 Adverse events.

6.4.3.4 History of symptomatology.

The subject will be questioned directly about the presence in general (since the last visit) of the following symptoms: pain and photophobia. Respond about the severity and frequency of symptoms such as:

Severity: Absent (0), very mild (1), mild (2), moderate (3) and severe (4)

Frequency: At all times (4), almost at all times (3), 50% of the time (2), almost at no time (1), at any time (0).

The number corresponding to each symptom will be registered in the CRF.

Symptomatology postinstillation:

The subject will be questioned if after applying the medication he felt burning, pruritus, a foreign body sensation and blurred vision.

Presence or absence: it will be marked as present (1) or absent (0) in the CRF for each of the symptoms questioned

Frequency: In all applications (4), almost in all applications (3), 50% of applications (2), almost in no application (1), in no application (0)

Duration: More than 5 minutes after the application (3), More than one minute but less than 5 (2), Less than one minute (1), Nothing (0).

The frequency and duration is for all the symptoms in general, the highest frequency and duration reported will be reported in the CRF.

6.4.3.5 Optical coherence tomography.

By means of optical coherence tomography (OCT) the GCR will be measured; Because this is a multicenter study it is not feasible to standardize the brand and model of the OCT to be used, it will allow the use of OCT Stratus (Carl Zeiss), Cirrus (Carl Zeiss), Spectralis (Heidelberg Engineering) with the minimum requirement that the baseline and final OCT are performed with the same OCT, with the same protocol and these characteristics are recorded in the clinical note and in the CRF, together with the central average.

6.4.3.6 Tonometry.

Tonometry is the objective measure of PIO, based primarily on the force required to flatten the cornea, or the degree of corneal indentation produced by a fixed force. Goldman's tonometry is based on the Imbert-Fick principle. [71]

The tonometry will be carried out, after instillation of the topical anesthetic, with fluorescein and the use of the cobalt blue filter (after the evaluation of the surface staining). There will be 2 shots and the average will be calculated, which will be recorded in the clinical file. The average will be registered in the CRF.

6.4.4 Measurement time.

- Measurements at the baseline visit

- Biomicroscopy
- Visual ability
- History of symptomatology
- OCT
- Tonometry
- Evaluation of adverse events
- Measurements in visit 1 and 2
- Biomicroscopy
- Visual ability
- Evaluation of adverse events
- History of symptomatology
- Tonometry
- Measurements in final visit
- Biomicroscopy
- Visual ability
- Adverse event evaluation
- History of symptomatology
- OCT
- Tonometry
- Measurements on security call
- Evaluation of adverse events

6.5 Schedule and study diagram.

The **baseline visit** will be considered on day 1 of the study and should be within the first 24 postoperative hours, the IP will indicate the subject to start the application of the investigational products that same day. If necessary, adjust the scheme so that it complies with the 4 applications of day 1; however, in the event that during the opening hours it is not feasible to adjust the 4 applications, the IP will indicate the application of at least 2 instillations, with a minimum of 2 hours between them.

Visit 1 will be performed in relation to the start of treatment on day 7 with a window period of ± 2 days.

The **visit 2 and final** will be made on days 14 and 29, respectively, with a window period of ± 2 days for visit 2 and + 3 days for the final.

The **security call** will be made on day 43, with a window period of ± 3 days.

